1.3 Secondary Study Endpoints

State the secondary endpoints to be measured in the study.

- Successful uptake and demonstrable utility of actigraphy and intermittent home-based blood pressure monitoring (HBPM) during and after pregnancy.
- Successful uptake and demonstrable utility of an enhanced smoking cessation intervention among women who smoke or have environmental smoke exposure.

2.0 Background

2.1 Scientific Background and Gaps

Describe the scientific background and gaps in current knowledge.

For clinical research studies being conducted at Penn State Health/Penn State College of Medicine, and for other non-PSH locations as applicable, describe the treatment/procedure that is considered standard of care (i.e., indicate how patients would be treated in non-investigational setting); and if applicable, indicate if the treatment, drug, or device is available to patient without taking part in the study.

Unhealthy lifestyles among women of reproductive age are threats to pregnant women, their offspring, and our nation's health.¹ ~70% of women of reproductive age have a component of metabolic syndrome and nearly 25% have three or more components,² with higher rates among non-Hispanic Black and Hispanic women.² >50% of women with metabolic syndrome in early pregnancy develop complications including preeclampsia and gestational diabetes (GDM).² Preeclampsia is associated with increased maternal chronic hypertension and cardiovascular disease (CVD) later in life, including congestive heart failure,³ myocardial infarction, and stroke.⁴ Women with GDM have an increased risk of diabetes (mostly type 2) later in life; up to 70% of women with GDM develop diabetes within 28 years of pregnancy;⁵⁻⁷ minorities have higher rates of GDM and shorter conversion times.⁸⁻¹⁰

Exposure to hypertensive disorders, diabetes, and obesity during gestation has lifelong impact on offspring health.¹¹ Poor maternal CVH during gestation is associated with higher risks of poor offspring CVH at ages 10-14 years.¹² Offspring of women with elevated BMI or metabolic dysfunction during pregnancy have greater adiposity, less favorable lipid profiles, higher blood pressure, and greater insulin resistance across childhood, and are at increased long-term risk of obesity, metabolic dysfunction, and CVD compared with offspring of women with low metabolic risk.¹³⁻³⁶ Preeclampsia increases risk for complications including intrauterine growth restriction, low birth weight, preterm birth, and neonatal death.³⁷ GDM increases risk of macrosomia, neonatal hypoglycemia, and birth trauma.^{38,39} Thus, maternal CVH is vitally important for offspring lifetime CVH,⁴⁰ yet few interventions during pregnancy and postpartum have focused on long term maternal CVH.

Perinatal HV programs have been utilized domestically and abroad since the 1800s through various models. Most use a multi-visit model encompassing both pre- and postnatal HV. The Nurse-Family Partnership (NFP) program is one of the most well regarded models,^{41,42} and is one of 21 models meeting federal criteria for evidence of effectiveness.⁴³ NFP serves vulnerable, low income, first-time mothers and seeks to improve health and social outcomes for mothers and infants.⁴⁴ Women enroll by week 28 of pregnancy, have weekly nurse visits for a month followed by twice monthly visits until delivery. After delivery, dyads are visited weekly for 6 weeks, then twice monthly until the infant is 21 months old. From ages 21 months to 2 years, visits are once per month.

Women who participate in NFP have improved knowledge about contraception, fewer subsequent pregnancies, and more time between pregnancies.⁴⁵⁻⁴⁹ Infants have fewer emergency visits, unintentional injuries, and poisonings^{47,50,51} with a reduced incidence of child abuse and neglect.^{46,50,52} Years after program completion, the positive effects persist,⁵³⁻⁵⁶ resulting in a cost-effective intervention due to less reliance on government-based financial assistance programs.⁵⁷ NFP accounts for contextual factors (e.g., mental health, substance use/abuse, cognitive limitations, etc.) that compromise mothers' abilities to protect themselves and their children, which in part accounts for the program's success. While HV programs cover CVH-related topics (e.g., prenatal diet, weight gain, cigarette smoking, etc.) these programs have not been particularly successful at improving maternal-child CVH. Nonetheless, the visit structure, opportunity for continual refinement, training infrastructure, and quality control mechanisms suggest untapped potential for improving maternal-child CVH.⁵⁸

Appalachia is among the most socioeconomically disadvantaged US regions with marked CVH disparities.⁵⁹ Obesity (>30%), smoking (>20%), and physical inactivity (>25%) are more common in Appalachian adults than in the US overall.⁶⁰⁻⁶³ Those in rural Appalachia are more likely to be obese, engage in unhealthy behaviors (i.e., poor diet, physical inactivity, smoking), and have poor mental health than those in metropolitan areas.⁶⁴⁻⁶⁶ As a result, heart disease, stroke, and diabetes are 17%, 14%, and 11% more common in Appalachia than the rest of the US with higher rates of hospitalization and mortality.⁶² Social determinants of health including poor access to preventive care, high rates of generational poverty, and low educational attainment along with reduced access to healthy, affordable foods contribute to the vast health disparities and set the stage for poor CVH.⁶⁷ Addressing social disparities is central to improving CVH and life expectancy.⁶⁸ This research targets Northern Appalachia where heart disease mortality is 13%

higher than the US rate and 11% higher than the rate in non-Appalachian Pennsylvania.⁶⁹ The targeted region contains a dozen HRSA-designated medically underserved areas/populations⁷⁰ and while government-sponsored insurance predominates, hesitancy to enroll in government programs is common, resulting in coverage and care gaps⁷¹ that contribute to poor CVH. Specific to the maternal-child population, women of childbearing age have poorer preconception health with higher rates of obesity, smoking, and poor nutrition compared with non-Appalachian women.⁷² They also have lower rates of annual checkups with healthcare providers.

Digital devices to track human health have become widely utilized both by individuals and in medical care. The sophistication, ease of use, accuracy and cost have improved dramatically in recent years. Continuous glucose monitoring has become the standard for managing patients with type 1 diabetes with immediate data access (now through the cloud) by caregivers to guide treatment doses and regimen.⁷³ We pioneered the use of continuous glucose monitoring during pregnancy in women with polycystic ovary syndrome and documented good correlations with concurrently conducted oral glucose tolerance tests in a cohort of women across four time points in pregnancy.⁷⁴ Such devices are ideal for prenatal care where biometric factors as maternal weight, maternal blood pressure and fetal heart rate are important prognostic factors for the pregnancy outcome and maternal and child health. All of these factors can be accurately tracked by digital devices and our team has had both extensive clinical and research experience utilizing them. The most important of these biometric factors is maternal blood pressure, as increases are suggestive of gestational hypertensive disorders. Elevated blood pressure is arguably the greatest risk factor for serious maternal morbidity and mortality through pre-eclampsia or eclampsia. Ambulatory Blood Pressure Monitoring (ABPM) has been studied extensively not only during pregnancy^{75,76} but for a number of cardiovascular conditions and has been found to correlate well with measures obtained in medical⁷⁷ settings and to correlate well with response to treatment and risk of cardiovascular events.⁷⁸ We have used 24 hour ABPM in a cohort study of women at risk for developing gestational hypertension throughout pregnancy (N = 73).⁷⁹ We found strong and significant correlation between measurements obtained through ABPM and those in the clinic. Further the strongest correlation was in those with the least risk, the population we are proposing to study in this proposal. Our results have been validated in meta-analyses of home blood pressure monitoring (HBPM), intermittent self-measurement of BP outside of a clinic setting) during pregnancy though most studies have used it in at risk populations to augment clinical measurements, instead of in lieu of clinical measurements as we are proposing.^{76,80} Meta-analysis has shown the use of HBPM is associated with significantly fewer antepartum visits, diagnoses of pre-eclampsia, pre-delivery hospital admissions and inductions with no difference in maternal and neonatal morbidity and mortality.^{76,80} Recently two large multi-center randomized controlled studies of AHBPM in pregnancy in an at risk population for gestational hypertensive disorders found no benefit in AHBPM in diagnosing such disorders earlier than the control clinic based population (BUMP 1)⁸¹ nor any benefit in AHBPM in reducing systolic blood pressure (BUMP 2).⁸² Our study will use periodic HBPM, to monitor all patients (many patients who develop these disorders have no risk factors) during pregnancy. This study will also monitor blood pressure across the transition from pregnancy to postpartum which will provide novel data about this understudied transition. Additionally, we will monitor steps with an accelerometer and movement/sleep with an actigraphy device as we have done in previous lifestyle intervention studies.

2.2 Previous Data

Describe any relevant preliminary data.

Multiple study team members have participated in lifestyle interventions for pregnant women to improve CVH outcomes. Drs. [name] and [name] collaborated on multiple preconception lifestyle interventions to decrease weight in women with overweight/obesity and to improve maternal pre-conception CVH. In *OWL-PCOS*,⁸³ those with polycystic ovarian syndrome-caused anovulatory infertility were assigned to receive either 16 weeks of 1) lifestyle modification consisting of caloric restriction with meal replacements, weight loss medication and increased physical activity ("Lifestyle"); 2) a weight loss neutral intervention of continuous oral contraceptive pills (OCP) or 3) "Combined" treatment with both. After preconception intervention, women underwent standardized ovulation induction with clomiphene citrate. A significant

preconception weight loss was achieved with both Lifestyle (mean weight loss -6.2%; 95%CI -7.4, -5.0%); and Combined (mean weight loss, -6.4%; 95%CI -7.6, -5.2%) compared with OCP (both $p<.001$). The OCP group had a significant increase in the prevalence of metabolic syndrome from baseline to the end of preconception treatment (OR, 2.47; 95%CI 1.42, 4.27) whereas no change in metabolic syndrome was detected in the Lifestyle or Combined groups. Ovulation and live births were also improved in the Lifestyle and Combined groups.

Healthy Moms, led by [name] was a randomized controlled trial of behavioral lifestyle-intervention started in pregnancy which aimed to limit gestational weight gain (GWG) and reduce offspring weight for gestational age at birth.⁸⁴ The intervention consisted of weekly groups sessions until delivery (16 week core curriculum modeled after DPP).⁸⁵ The intervention focused on healthy eating (following DASH diet), getting adequate exercise (goal of 30 minutes or 10,000 steps daily), and behavioral self-management techniques.⁸⁶ Women with obesity were randomized between 7 to 21 weeks' gestation to intervention or usual care. Intervention participants gained less weight from randomization to 34 weeks gestation (5.0 vs. 8.4 kg, mean difference=-3.4 kg; 95%CI -5.1, -1.8), and from randomization to 2 weeks postpartum (-2.6 vs. +1.2 kg, mean difference=-3.8 kg; 95%CI -5.9, -1.7). They also had fewer large for gestational age newborns (9% vs. 26%, OR=0.28; 95%CI 0.09, 0.84).

As for tobacco cessation, [name] is an international expert, and we suggest that a longitudinal care approach modeled on principles of chronic disease management is more effective than a discrete episode of state-of-the-science treatment to promote prolonged abstinence.⁸⁷⁻⁹⁰ This includes a state-of-the art psychoeducational intervention based on existing NFP evidence-based protocols that includes health education, motivational interviewing and counseling.⁹¹

Recently the American Heart Association added sleep as one of the key measures for improving and maintaining cardiovascular health expanding the Life's Simple Seven to the new rubric of Life's Essential Eight. The AHA recommended a minimum of 7 hours sleep with a range of 7-9 hours.⁹² Less sleep is associated with the development of an adverse cardiovascular risk profile. It can also be tracked via actigraphy device and is modifiable.

Our group's extensive experience with these interventions from design to implementation to dissemination will help us adapt them to evidence based HV models.

2.3 Study Rationale

Provide the scientific rationale for the research.

This trial will pilot the enhanced version of the Nurse Family Partnership standard care plan to promote greater cardiovascular health in mothers by targeting decreased sedentary time and enhanced activity (and where applicable smoking cessation) during and after pregnancy. We will also pilot the feasibility and acceptability of digital devices (e.g., actigraphy, digital scale, blood pressure monitor) during this same time period.

3.0 Inclusion and Exclusion Criteria

Create a numbered list below in sections 3.1 and 3.2 of criteria subjects must meet to be eligible for study enrollment (e.g., age, gender, diagnosis, etc.).

Vulnerable Populations:

Indicate specifically whether you will include any of the following vulnerable populations in this research. You MAY NOT include members of these populations as subjects in your research unless you indicate this in your inclusion criteria because specific regulations apply to studies that involve vulnerable populations.

The checklists referenced below outline the determinations to be made by the IRB when reviewing research involving these populations. Review the checklists as these will help to inform your responses throughout the remainder of the protocol.

- **Children** –Review “HRP-416- Checklist - Children”
- **Pregnant Women** – Review “HRP-412- Checklist - Pregnant Women”
- **Cognitively Impaired Adults**- Review “HRP-417- Checklist - Cognitively Impaired Adults”
- **Prisoners**- Review “HRP-415- Checklist - Prisoners”
- **Neonates of uncertain viability or non-viable neonates**- Review “HRP-413- Checklist - Non-Viable Neonates” or “HRP-414- Checklist - Neonates of Uncertain Viability”

[Do not type here]

3.1 Inclusion Criteria

Create a numbered list of the inclusion criteria that define who will be included in your final study sample (e.g., age, gender, condition, etc.)

1. Enrolled in and receiving the Nurse-Family Partnership program through the Geisinger Clinic or UPMC Home Health Care of Central PA
2. Age \geq 18 years old
3. Nulliparous pregnant woman
4. Women with a singleton viable pregnancy confirmed by NFP home visitors
5. English speaking
6. Access to reliable internet service required for data collection
7. Willingness to download and access an app on personal smartphone
8. A minimum of 5 women with use of nicotine containing products (cigarette, cigar, hookah, chewing tobacco, e-cigarette, patch) within the past 3 months

3.2 Exclusion Criteria

Create a numbered list of the exclusion criteria that define who will be excluded in your study.

1. Unable or unwilling to comply with the study visits and procedures
2. Diagnosis of cancer
3. A personal history of complex congenital heart disease
4. A fetus in the current pregnancy with known chromosomal abnormalities or birth defects inconsistent with survival to 2 years will be excluded
5. Participation in a concurrent intervention study

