4.1 Identification of subjects

Describe the source of subjects and the methods that will be used to identify potential subjects (e.g., organizational listservs, established recruitment databases, subject pools, medical or school records, interactions during a clinic visit, etc.). If not recruiting subjects directly (e.g., database query for eligible records or samples) state what will be queried, how and by whom.

StudyFinder:

- If you intend to use StudyFinder (<http://studyfinder.psu.edu>) for recruitment purposes, include this method in this section.
- Information provided in this protocol needs to be consistent with information provided on the StudyFinder page in your CATS IRB study.

For Penn State Health submissions using Enterprise Information Management (EIM) for recruitment, and for non-Hershey locations as applicable, attach your EIM Design Specification form on in CATS IRB (<http://irb.psu.edu>). See “HRP-103- Investigator Manual, What is appropriate for study recruitment?” for additional information. **DO NOT** include the actual recruitment material or wording in this protocol.

Participants meeting inclusion/exclusion criteria will be those participating in the NFP program through the Geisinger Clinic or UPMC Home Healthcare of Central PA. Potential participants who are <28 weeks' gestation and at least five potential participants who have used nicotine containing products in the past 3 months will be identified by visiting nurses and/or their supervisors.

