All NFP visiting nurses participating in this study will be trained in screening procedures. No Protected Health Information (PHI) will be collected during screening procedures. Potential participants will be approached by NFP visiting nurses during regularly scheduled home visits. NFP visiting nurses will provide recruitment materials that include information about the study with potential participants and verbal consent will be obtained before any screening questions are asked of participants. Once a potential participant is deemed eligible after screening and expresses interest in participating, written informed consent will be obtained. Information collected as part of screening procedures will only be used to assess eligibility and will not be used in research analyses.

****Site Congruency: Is the information provided in the above section (Recruitment Methods) consistent across all relying sites in this research?**

Yes

No - Identify the sites that have dissimilar procedures: *[This field should solely identify the site. Dissimilar procedures across sites should be identified in the SITE workspace via HRP-XXX – R2S Site Plan]*
[Type protocol text here]

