5.2 Obtaining Informed Consent

5.2.1 Timing and Location of Consent

Describe where and when the consent process will take place.

Potential participants will receive information about the study during a regularly scheduled NFP home visit. If eligible and interested in participating, study personnel ([NFP nurses](#)) will provide the IRB-approved informed consent form and written consent will be obtained (signed consent and/or electronic consent). NFP nurses will be added as study personnel and will perform the entire informed consent process from explaining the study to obtaining written consent.

We will pilot the feasibility of obtaining written and/or electronic consent. E-consent will be obtained via PSHMC's secure REDCap database and will include electronic signatures and real-time timestamps. REDCap's e-consent framework allows participants to receive a signed copy of the consent form via email or we will print and send a copy upon request.

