7.2 Study Procedures

Provide a step by step description of all research procedures being conducted (broken down by visit, if applicable) including such information as below (where and when applicable); describe the following:

- HOW: (e.g., data collection via interviews, focus groups, forms such as surveys and questionnaires, medical/school records, audio/video/digital recordings, photographs, EKG procedures, MRI, mobile

- devices such as electronic tablets/cell phones, observations, collection of specimens, experimental drug/device testing, manipulation of behavior/use of deception, computer games, etc.)
- WHERE: (e.g., classrooms, labs, internet/online, places of business, medical settings, public spaces, etc.)

Intervention Overview. Our pilot CVH intervention will be delivered by NFP visiting nurses starting as early as NFP program enrollment in the first trimester after confirmation of a viable pregnancy and no later than the 28th week of pregnancy and will continue up to 6 months postpartum. The visit schedule will be consistent with the NFP program visit structure to deliver intervention content at regularly scheduled visits that are typically 60 minutes long (weekly visits for the first month following enrollment followed by twice monthly visits until delivery).

The pilot intervention will include a behavioral component aimed at reducing sedentary behaviors as well as utilizing a technology/monitoring component. We will monitor all mothers with a wrist-worn actigraphy device (FitBit) to record activity and sleep, weight scale (Fitbit Scale), intermittent home ambulatory blood pressure self-monitoring (HBPM), and carbon monoxide monitoring administered by the NFP visiting nurse. Carbon monoxide monitoring is part of an attempt to reduce the use of nicotine-containing products. Monitoring with digital devices is discussed below and in the digital device section which follows a description of the interventions. However, the participant will have access to the digital data on the device through smartphone or computer apps to reinforce desired behaviors.

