8.3 Statistical methods

Describe the statistical methods (or non-statistical methods of analysis) that will be employed.

Descriptive statistics for surveys as well as feasibility (e.g., recruitment and retention, fidelity, data collection methods) and acceptability (e.g., satisfaction) will be calculated.

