15.2 Feasibility of recruiting the required number of subjects

Indicate the number of potential subjects to which the PSU study team has access. Indicate the percentage of those potential subjects needed for recruitment.

Given the small sample size for this pilot study, it is feasible to recruit the number of subjects needed. Our two NFP agency partners enroll several hundred pregnant women into their programs annually. The Center for Childhood Obesity Research (CCOR) has previous experience recruiting pregnant women and women who have recently delivered and has long standing working relationship with Geisinger and UPMC offices across the state.

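### Exclusion 1 and discretionary identification allow women expected to comply poorly to be left out of a pilot that reports acceptability, uptake and retention, and no screening tally would show it

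*Combined protocol and SAP*

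**What the plan says.** Item 1 of section 3.2 excludes any woman "Unable or unwilling to comply with the study visits and procedures". No definition follows, and no assessor is named.

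Section 4.1 says that potential participants "will be identified by visiting nurses and/or their supervisors". Sections 4.2.1 and 17.4 repeat this. None of them requires that all eligible clients be approached, or sets an order.

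The nurses' other roles are these:
- Approach: "Potential participants will be approached by NFP visiting nurses during regularly scheduled home visits" (section 4.2).
- Screening: "All NFP visiting nurses participating in this study will be trained in screening procedures" (section 4.2).
- Consent: the nurses "will perform the entire informed consent process from explaining the study to obtaining written consent" (section 5.2.1).
- Delivery: "Our pilot CVH intervention will be delivered by NFP visiting nurses" (section 7.2). Under the same section they also document participant engagement and quality of delivery.

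On outcomes, section 1.2 makes good acceptability to nurses and participants a primary endpoint, together with consent of 20 women. Section 1.3 makes uptake of actigraphy and home blood pressure monitoring secondary. Section 8.3 plans descriptive statistics for "feasibility (e.g., recruitment and retention, fidelity, data collection methods", as well as for acceptability.

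Section 4.2.4 restricts information gathered at screening to the eligibility decision and keeps it out of research analyses. The protocol describes no log of women eligible, approached, excluded or declining.

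**The concern.** In an efficacy trial, a clause excluding people unable to comply is common and often harmless. Here, how well women take up, tolerate and stay with the procedures is the result. A woman left out because she is expected to miss visits or not use the blood pressure monitor is a woman whose experience the pilot exists to record.

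Two routes lead to the same place. Exclusion 1 permits such a woman to be screened out. Discretionary identification permits her never to be approached, so she would not appear even as a screen failure.

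The pilot is meant to inform a large multi-site trial (section 11.2). If retention, blood pressure monitoring uptake or satisfaction come from a favourable subset, that trial could be planned on optimistic figures. Reaching 20 consents would also say little about recruitability without knowing how many women were eligible and approached.

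**Working it through.** There is no design figure to reproduce: section 8.1 gives 20 women and section 8.2 states that no formal sample size calculation was made. The check is therefore a comparison of sections, followed by an illustration of size.

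**Step 1. Entry rules against outputs.** Section 3.2 filters on ability to comply with visits and procedures. Sections 1.2, 1.3 and 8.3 report acceptability, uptake and retention, all of which depend on that ability. The filter and the outputs overlap.

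**Step 2. Before entry against after entry.** Section 3.3.1 allows removal only for withdrawal of consent or for safety, so poor adherence after consent stays in the data. Section 3.3.2 keeps all data up to withdrawal. The plan thus treats non-adherence as information once a woman is in, but allows expected non-adherence to keep her out.

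**Step 3. Can the effect be seen afterwards?** Section 8.3 promises recruitment as a feasibility measure. A recruitment rate needs a denominator of women eligible or approached. Section 4.2.4 bars screening information from analysis and no log is described, so only the numerator is assured.

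**Step 4. Illustration of size.** Let p be the completion rate among all eligible women, s the share of would-be non-completers left out, and f the share of would-be completers left out. All three are assumptions; the documents give none of them. Expected completion among those enrolled is

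q = p(1 − f) / [p(1 − f) + (1 − p)(1 − s)].

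With p = 0.60, s = 0.50, f = 0: q = 0.60 / (0.60 + 0.40 × 0.50) = 0.60 / 0.80 = 75.0%.

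Over a range of p and s, with f = 0:

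| p | s = 25% | s = 50% | s = 75% |
|---|---|---|---|
| 50% | 57.1% | 66.7% | 80.0% |
| 60% | 66.7% | 75.0% | 85.7% |
| 70% | 75.7% | 82.4% | 90.3% |
| 80% | 84.2% | 88.9% | 94.1% |

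If selection also wrongly loses a quarter of completers (p = 0.60, s = 0.50, f = 0.25): q = 0.45 / (0.45 + 0.20) = 69.2%. If s = f, the factors cancel and q = p. The bias is upward only if the judgement identifies non-completers better than chance.

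**Step 5. What a reader would see.** The plan sets no success threshold, so take 16 of 20 purely as an example. The binomial chance of at least 16 completers is 5.1% at 60% and 41.5% at 75%. The exact 95% interval around 16/20 is 56% to 94%. It reflects sampling error only and makes no allowance for selection.

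**The case against.** The strongest reply is that the documents show an opportunity for selection and not that it happens. No section says who judges a woman unable, and supervisors may identify candidates as well as nurses. Screening by questions put to the woman, which section 4.2.4 describes, is compatible with simple self-report of availability. This stands, and it limits the point to what the wording permits.

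Four stronger readings are tempting, and the documents do not support them.
- *Nurses already know each client's attendance record and will choose the reliable ones.* No section says so. Section 7.2 lets the module start as early as NFP enrolment, when there may be little history to know.
- *The nurses have very wide room to choose.* Section 15.2 says "Our two NFP agency partners enroll several hundred pregnant women into their programs annually". If that meant 200 to 500 women (an assumption), 20 would be 10% to 4% of intake. But this is total intake at both agencies. Aim 2 trains only selected nurses, and sections 3.1 and 4.1 restrict candidates by age, gestation, language, internet access and app use. The relevant denominator is the eligible caseload of those nurses, which is not given.
- *Retention would be reported as 18/20 instead of 14/20.* Those counts only restate assumed rates of 90% and 70%.
- *The sample is selected on its primary outcomes throughout.* Of the quantities at issue, acceptability is primary and uptake secondary; retention is named only in section 8.3. Fitbit and scale data are not collected for research (section 7.2), so inflation of recorded device use is largely moot for those two devices.

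It is also fair to say that part of the clause is redundant (unwilling women will decline consent) and part may be factual, such as a planned move. Inclusions 6 and 7 filter on internet access and app willingness too. Those are stated conditions that can be counted and reported, unlike an undefined expectation of poor compliance.

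**Conclusion.** The point holds as a weakness in the entry rules. Exclusion 1 and discretionary identification together allow women expected to comply poorly to be left out of a pilot that reports acceptability, blood pressure monitoring uptake, recruitment and retention. Those results could be biased upward. The documents do not show that they will be, and they give nothing from which the size can be estimated.

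The step from 60% to 75% shows what moderate selection could do, on assumed values. The direction rests on one further assumption, that the judgement about who would comply is better than chance. With 20 women and purely descriptive analysis, no analytic correction is available, and without a screening tally the selection could not even be described. For so small a pilot this is a modest fault, but the remedy is nearly free and should be adopted.

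**What to change.** 1. **Section 3.2.** Remove expected non-compliance as a reason for exclusion. Refusal is already covered by consent. Either delete item 1 or limit inability to listed factual reasons, such as a planned move or leaving NFP.
2. **Sections 4.1 and 4.2.1.** Require each participating nurse to approach every otherwise eligible client under 28 weeks on her caseload, in order of scheduled visit, until 20 have consented. State in advance how places are reserved for the minimum of 5 recent nicotine users. For example, cap women without recent use at 20 − 5 = 15 and keep visit order within each group. This departs slightly from a single consecutive series, so it should be written down and counted.
3. **Section 4.2.4.** Amend the restriction so that a de-identified count of women eligible, approached, excluded (with reason, including inclusions 6 and 7), declined and consented can be reported. Add those counts to the descriptive outputs in section 8.3.

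Cost: protocol wording, a line in nurse training and a short tally for nurses to keep, with no extra study visits. Reported retention and uptake may be lower than under the present wording.
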